- The Study Coordinator will keep hand sanitizer in their car and use before and after delivery of assessment and programmatic materials.
- The research team will follow all safety protocols instituted by the University of Colorado regarding COVID-19 and human subjects research.

Weight Gain. Weight will be collected at T1 and T3 for all intervention and control participants. Participants will be asked to record their weight three times on one day and send a picture (via text or email) to a member of the research team during the 7-day assessment week. Individuals will be asked to remove their clothes and shoes and keep on their undergarments and weigh themselves first thing in the morning before they eat anything. Total GWG will be captured three times consecutively and then averaged across these three weight recordings. Total GWG will be compared to the IOM guidelines at T1

and T3 and calculated as: +, -, or 0 with respect to the guidelines (based on each woman's pre-pregnancy BMI-determined GWG category) such as GWG above the guidelines (+), below guidelines (-), or within the guidelines (0) [39]. Participants randomized to the intervention group will also be given a TANITA scale to measure weight at home daily (the research team will send weekly reminders via email or text). Women will step on the scale and note their weight on a tracking log at the same time each day. Participants will email copies of tracking logs weekly to the study coordinator. Please see appendix for tracking log.

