Sample Size. In terms of intervention effects on EGWG, results have been variable across studies, with average intervention effects being small to moderate. In terms of physical activity, our preliminary work with the original MBMM showed an effect roughly equivalent to Cohen's $d = 0.69$. This effect falls into the moderate range, similar to higher-impact interventions on EGWG [27]. Based on these two effect ranges, we estimated effect size to detect effects of $d > .63$, a medium effect, for the proposed MBMM+ intervention. Using this effect size, $\alpha = .05$, and $1-\beta = .80$, a sample size of 40 per arm (80 total) would be adequate to detect medium effects in EGWG, exercise, and other outcomes. We propose enrolling 50 per arm to account for up to 20% attrition and to allow for power to detect potentially smaller effects for EGWG. This level of power is expected to also be adequate for detecting changes in mediators, which have previously been observed to be more powerfully affected by the MBMM intervention than physical activity.

Due to COVID-19, the trial will be run two times; a remote pilot of the trial will be run in the Fall of 2020 (n=30), followed by a larger in-person trial (pending COVID-19) in the Spring of 2021 (n=70)

C. Study Design and Research Methods

Intervention Group:

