Recruitment and Informed Consent. The proposed study will utilize recruitment strategies that were found to be effective during formative work and are described in the research plan. Participants will be recruited actively via clinicians at obstetric clinics. An informational flyer will be shared with all potentially eligible women and women will sign-up during check-out if they are interested in the program. Program staff will contact interested women and ask pre-screening questions to assess eligibility. Participants will also be recruited passively via informational flyers; these flyers will contain research team contact information and will be displayed in public spaces at clinics and in community settings and on listservs/internet sites. Potential participants can email or call a member of the research team to learn more about the study and participate. We are confident that we will be able to recruit the necessary sample to conduct the proposed work based on our working relationship with local clinics. All eligible participants will need to sign a HIPPA waiver with the doctor to enable medical information to be released to the study team as well as a waiver stating that they are cleared for physical activity. All eligible participants will be asked to complete a consent form and baseline survey (comprised of all T1 tools mentioned above) remotely. Once this is completed, participants will receive a Fitbit and a scale and complete the 7-day Fitbit assessment period. They will take their weight (three times) one day during this period and send an email or text to the Study Coordinator. The consent form describes the purpose of the study, criteria for participation, confidentiality measures, incentive details, and contact information for the principal investigator. Contact information will be stored separately from the surveys such that it could not be linked to survey responses. Upon completion of the baseline survey (T1) and the 7-day Fitbit assessment period, participants will be randomly assigned to either the intervention (MBMM+ program) or control arm (i.e. health education program) using computer generated numbers and assigned from a pre-generated table.

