Inclusion criteria – The population of interest includes English-speaking, pregnant (<13 weeks gestation; or 13-16 weeks gestation and has gained less than 10 lbs in total for women of normal pre-pregnancy weight or less than 5 lbs for overweight/obese) primiparous women, aged 18-46 years, reside in Denver, CO and have medical clearance to exercise during pregnancy. Exclusion criteria include multiparous and having conditions that preclude them from exercising (i.e. HCP has restricted patient from engaging in exercise according to AGOG's absolute contraindications to exercise (e.g. haemodynamically significant heart disease, restrictive lung disease, incompetent cervix/cerclage, persistent second or third trimester bleeding, placenta previa after 26 weeks gestation, premature labor during the current pregnancy, ruptured membranes, and pregnancy induced hypertension).

Protection Against Risk. Every effort will be made to ensure the protection of participants against risk. First, participation is voluntary and participants may refuse to participate or withdraw from the study at any time. Second, participants do not waive any legal rights by consenting to the study. Third, the Principal Investigator and program manager will be

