Throughout the course of this study, we will provide for protection of human subjects. All protocols will be submitted for review and approval to the Colorado Multiple Institution Review Board (COMIRB). All personal data will be kept secure with personal identifiers and study identification numbers maintained in separate, secure, databases. Only the PI and Co-Is will have access. The proposed study is designed to women and overall, the findings of this study may potentially impact the health and wellbeing of women and children.

We have also designed the assessment procedures to minimize burden on participants. Participants will be compensated \$30 per survey completion (T1 and T3; \$60 total/participant). Participants will also receive tickets for a random drawing and chance to receive free diapers for their participation in T2 data collection. Pregnant participants in the MBMM+ intervention group will also receive a yoga mat and pedometer, and both control and intervention groups will receive drawings for free diapers. These types of incentives and amounts are consistent with our other studies at UCH. In addition to the yoga mat and pedometer, the intervention group participants will have the opportunity to keep a Fitbit. If participants attend all sessions 8-16, they will get to keep a Fitbit at the end of the program following post-data collection. If participants in the intervention program attend all but two sessions from sessions 8-16, they will be entered into a raffle for a Fitbit to keep at the end of the program following post-data collection.

F. Data Analysis Plan:

We will use latent growth curve models to separately examine intervention effects on 1) moderate-intensity exercise assessed by the Fitbit and 2) EGWG. These models will then be expanded to examine secondary outcomes (e.g., physical activity, mood, sleep quality, delivery outcomes) and mediators (e.g., exercise self-efficacy, social support, and behavioral skills). For all models, we will control for patient age, ethnicity, parity, risk status, and SES. Primary analyses will be conducted as intent-to-treat, although exploratory as-treated analyses may also be used. Analyses will be conducted primarily using SAS Version 9.2 and Mplus Version 6.0. In closing, the study's proposed approach

is scientifically sound using a tight, randomized controlled trial framework to reduce study bias and increase likelihood of reproducibility.

G. Summarize Knowledge to be Gained:

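### The covariate list for all models omits run and pre-pregnancy BMI, and nothing in the allocation text assures balance on either; the cost is precision, not bias

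*Combined protocol and SAP*

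**What the plan says.** Four parts of the combined protocol and SAP bear on this point.

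- **Covariates (IV.F, Data Analysis Plan).** Latent growth curve models are planned for Fitbit exercise and for EGWG, and then extended to secondary outcomes and mediators. For every model, "we will control for patient age, ethnicity, parity, risk status, and SES". Neither run nor pre-pregnancy BMI is named, and risk status is not defined anywhere.
- **Role of BMI (IV.A, Weight Gain; IV.D, Inclusion criteria).** Weight gain is classed as above, within or below guideline, "based on each woman's pre-pregnancy BMI-determined GWG category". BMI also enters eligibility: at 13-16 weeks the limit on weight already gained is 10 lb for women of normal pre-pregnancy weight and "less than 5 lbs for overweight/obese". The same criteria admit primiparous women and exclude multiparous women.
- **Size and runs (IV.B, Sample Size).** The text states that "a sample size of 40 per arm (80 total) would be adequate to detect medium effects" and then: "We propose enrolling 50 per arm to account for up to 20% attrition". The trial is run twice, with 30 women remotely and then 70 in person if COVID-19 allows.
- **Allocation (IV.D, Recruitment and Informed Consent).** "Upon completion of the baseline survey (T1) and the 7-day Fitbit assessment period, participants will be randomly assigned" to one of the two arms, "using computer generated numbers and assigned from a pre-generated table". This is the only allocation text. It gives no ratio, blocking, strata, holder of the table or concealment step.

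**The concern.** Aim 2 is an effect-size estimate for a later, larger trial, taken from about 80 analysed women. Two baseline factors stand out in this design. Pre-pregnancy BMI category sets the range against which each woman's gain is judged. Run marks a planned change in delivery mode and season. Both are known for every woman before assignment.

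A plan can deal with such factors by balancing them at allocation, by adjusting for them in the model, or both. Here the allocation text does not promise balance and the covariate list names neither factor. One place in that list goes to parity, which the entry criteria hold constant. A second goes to a term that cannot be interpreted as written. What is at stake is avoidable noise in the main estimate, and an adjusted analysis that two analysts could carry out differently.

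**Working it through.** **1. The plan's own figure.** Inputs from Sample Size: d = 0.63, alpha = 0.05 (two-sided assumed; sidedness is not stated), power 0.80, attrition 20%.

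- n per arm = 2(1.960 + 0.842)² / 0.63² = 39.6, so 40. A one-sided test would need 32, so two-sided is the match.
- Enrolment = 40 / 0.80 = 50 per arm. Both stated figures reproduce.
- SE of d at 40 per arm = √(2/40) = 0.224. Power = Φ(0.63/0.224 − 1.96) = 0.804.

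**2. Does unequal arm size matter?** Suppose the list is simple and gives 40/60. After 20% attrition that leaves 32/48. SE = √(1/32 + 1/48) = 0.228, and power = Φ(0.63/0.228 − 1.96) = 0.788. The loss is 0.804 − 0.788 = 0.016. A split of 60/40 or worse has probability 0.057 under simple 1:1 allocation, so arm size is a minor matter.

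**3. How likely is imbalance on the two factors?** Simple 1:1 allocation is assumed, because the documents do not state the method.

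| Factor | Gap between arms | n = 100 | Run of 30 |
|---|---|---|---|
| BMI group, assumed prevalence 50% | 15 points or more | about 0.14 | about 0.41 |
| Share of women from the remote run | 10 points or more | 0.29 | not applicable |
| Share of women from the remote run | 20 points or more | 0.03 | not applicable |

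The BMI figures come from simulation. Forcing a 50/50 split without strata does not remove the problem: for an assumed prevalence of 30-60%, a BMI gap of 10 points or more at n=100 then has probability 0.27-0.32, against 0.29-0.37 under simple allocation.

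**4. What would a 15-point BMI gap do?** Assume that mean gain over 12 weeks differs by 0.5 SD between BMI groups (range 0.3-0.7). The documents give no figure.

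- Shift in the unadjusted effect = 0.15 × 0.5 = 0.075 SD (0.15 × 0.3 = 0.045; 0.15 × 0.7 = 0.105).
- Relative to the standard error: 0.075 / 0.224 = 0.33 (0.20-0.47).
- Variance explained at 50% prevalence = 0.5 × 0.5 × 0.5² = 0.0625. Leaving BMI out inflates the standard error by 1/√(1 − 0.0625) = 1.03, or about 3%.

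No comparable shift can be given for run, because the documents offer no basis for the size of its effect.

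**5. What does adjustment return?** If BMI explains a share R² of outcome variance, power at 40 per arm = Φ(0.63 / (0.224√(1 − R²)) − 1.96).

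- R² = 0.05: 0.824
- R² = 0.10: 0.844
- No adjustment: 0.804

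**The case against.** The strongest reply has four parts.

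- **The allocation text is silent, not defective.** A table made in advance may be blocked, stratified and hidden, and the statement "We propose enrolling 50 per arm" fits a restricted list at least as well as a simple one. This stands. A reader might infer a single open table without blocks or concealment, with staff able to select women by arm. The documents do not say that. Assignment follows the T1 survey and the Fitbit week, eligibility is confirmed before equipment is delivered, and the 13-16 week rule is a numeric limit. What can be said is that ratio, blocks, strata and list holder are not specified.
- **Chance imbalance is not bias.** This also stands. Under valid randomization it is already reflected in the confidence interval, and a shift of one third of a standard error is modest.
- **Classing gain against a BMI-specific guideline already takes BMI into account.** This stands in part. The 0.075 SD figure concerns gain on a continuous scale, and no shift has been shown for the three-level classification. The plan does not say which form enters the EGWG model.
- **Risk status may include BMI.** It may, but an undefined term cannot be relied on for that. It gives no cover for run.

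**Conclusion.** The point holds as a gap in the adjustment rule that the plan does state. Run is missing from the covariate list. Pre-pregnancy BMI is also missing unless risk status is meant to cover it. Parity should not vary in this population and so adds nothing. Balance on run and BMI is not assured by the allocation text.

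The size is modest. On the assumptions of simple 1:1 allocation, 50% prevalence and a 0.5 SD difference, about one trial in seven would show a BMI gap of 15 points or more overall. The resulting shift would be about one third of the standard error of d. The run of 30 is much more exposed if it is looked at separately.

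Two stronger readings should be set aside. One is that the estimate would be biased; the documents do not show failed concealment, and chance imbalance alone costs only precision. The other is that 50 per arm is under threat; even a 40/60 split costs less than 2 points of power. The case for change rests on how cheap the gain is, not on the size of the harm.

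**What to change.** **Data Analysis Plan.** In the EGWG and exercise models, replace parity with run and pre-pregnancy BMI. Enter BMI as a continuous variable, or by guideline category so that underweight women, whom the entry criteria do not exclude, are covered. Define risk status and say whether it includes weight category. The cost is one degree of freedom for run and one for continuous BMI (slightly more by category). It needs no extra women or visits, because both factors are already needed or known at baseline.

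**Recruitment and Informed Consent.** For any allocation still to be made, state the ratio, generate the list within run in permuted blocks of varying size, stratify by BMI group, name who holds the list, and state that recruiting staff cannot see it. Strata should be few, given the small runs. As an illustration, blocks of 4 within run and two BMI groups give 46/54 at worst, with power 0.802 after 20% attrition, so the sample size need not rise.

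The document is dated 5.6.21, while the sample-size text places the first run in Fall 2020. The allocation change cannot reach women already randomized. For them, state how the table was made and held, and rely on the covariate change.

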Physical activity. All participants (intervention and control) will wear a Fitbit Charge 3, which is a wrist worn physical activity tracker, for a 7-day period during T1 and T3. Fitbit counts the minutes of activity/steps each day. The use of Fitbit devices have been validated in pregnant women (St-Laurent, Mony, Mathieu, & Ruchat, 2018). Activity will also be formally assessed with all participants using an adapted version of the *Leisure-Time Exercise Questionnaire (LTEQ)*; Godin & Shepherd, 1985) at three time points (T1, T2, and T3). Additionally, participants will be assessed using the short form of the International Physical Activity Questionnaire (IPAQ; Hallal, 2004). Participants will complete the consent and survey electronically prior to the Fitbit and Scale delivery. Women will be asked to report how many days per week and minutes per day they engaged in regular exercise behavior. Reported minutes per day will be multiplied by days per week to calculate minutes per week of regular exercise behavior. The LTEQ is a valid and reliable measure of leisure-time exercise behavior (Godin & Shepherd, 1985) and has been used with pregnant women to better understand their exercise behavior (Sattler et al., 2018). Although, primary outcome physical activity data will be assessed by the Fitbit, LTEQ data will help further describe modes and intensities of physical activities. Women randomized to the intervention arm of the study will also informally track their daily physical activity on a tracking log. Participants will email copies of tracking logs weekly to the study coordinator.

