Nutrition. Nutrition-related behaviors will be formally assessed in all participants at T1 and T3. The Three Factor Eating Questionnaire is a 51-item questionnaire developed by Stunkard and Messick (1985) to measure three dimensions of human eating behavior: 1) dietary restraint, or cognitive control of eating behavior, 2) dietary disinhibition, or disinhibition of cognitive control of eating, and 3) susceptibility to hunger. We will only use 18 items of the revised TFEQ from Cappelleri (2009). Participants will complete the consent and survey electronically prior to the Fitbit and Scale delivery.

Theoretical Mediators.

1) A modified version of the Exercise Self-Efficacy scale [47] will be used to assess participants' beliefs in their ability to participate in physical activity. Internal consistencies are good (Cronbach's $\alpha = .99$ across time points). All participants will complete this tool at T1 and T3. 2) Behavioral Skills (e.g. self-regulation) will be assessed using three tools: 1) a 15-item subscale used in Project Grad [48], 2) the Pregnancy Weight Gain and Attitude Scale (PWGAS) ([name], 2003, 2004), and 3) a 3-item scale to assess perceived behavioral control ([name], 2003, 2004). All participants will complete these tools at T1 and T3 3) Social support for physical activity will be measured using two tools: 1) Social Support and Physical activity Scale [49] which assesses perceived social support from both family and friends on a 13-item scale, and 2) the General Social Support Questionnaire (SSW) which measures social support and satisfaction with social support. The SSQ has good test-retest reliability and convergent internal construct validity. All participants will complete these tools at T1 and T3.

Delivery outcomes (i.e., delivery type (vaginal vs. caesarian section), birth weight and gestational age, intervention used (if any), and maternal weight at delivery) will be assessed via self-report survey through REDCap.

Demographics

Socio-demographics (e.g., race/ethnicity, marital status, age, parity, income, education, insurance coverage) will be assessed via baseline survey at T1.

Optional data collection procedures

Participants may be contacted at the conclusion of the study and given the opportunity to choose to participate in a phone or zoom interview to better understand their thoughts about

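### Section IV.F names growth curve models for outcomes taken only at T1 and T3: the usual form is not identified on two waves, and the plan states no constraint and no rule on arm and baseline

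*Combined protocol and SAP*

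**What the plan says.** Section IV.F (Data Analysis Plan) gives the method in one sentence: "We will use latent growth curve models to separately examine intervention effects on 1) moderate-intensity exercise assessed by the Fitbit and 2) EGWG". It then extends the models to secondary outcomes and to the mediators, and adds: "For all models, we will control for patient age, ethnicity, parity, risk status, and SES". It gives no time score, random-effect structure or residual constraint, and does not say whether arm predicts the intercept.

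Section IV.A sets the schedule:

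- **Weight:** "Weight will be collected at T1 and T3 for all intervention and control participants". The three weighings at each wave are averaged to one value. Gain is then also "calculated as: +, -, or 0 with respect to the guidelines", using each woman's "pre-pregnancy BMI-determined GWG category".
- **Fitbit:** worn by both arms "for a 7-day period during T1 and T3".
- **Mediators:** the behavioural-skills and social-support scales carry the line "All participants will complete these tools at T1 and T3", and self-efficacy has the same two waves.
- **Three waves (T1, T2, T3):** only the LTEQ, the mood scales and the PSQI.

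Daily home weights are kept in the intervention arm only. A self-reported maternal weight at delivery (T4) is listed among the delivery outcomes, which IV.F treats as secondary. Table 1, the assessment timeline, is not in the text available to me, so the waves come from the prose of IV.A.

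**The concern.** A growth curve model separates each woman's true trajectory from occasion-to-occasion noise. Two observations per woman do not carry enough information to do that, so the usual model cannot be fitted to the Fitbit, weight or mediator data without a further constraint. The analyst must choose that constraint, and must also decide whether arm may predict the baseline level.

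Aim 2 exists to give an effect-size estimate for a larger trial. If these choices are made after the data are seen, the reported estimate and its standard error depend on decisions the plan did not fix.

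**Working it through.** **The plan's own figure.** The Sample Size paragraph uses d = 0.63, alpha 0.05 and power 0.80 (two-sided assumed). n per arm = 2 × ((1.960 + 0.842)/0.63)² = 39.55, so 40; and 40/(1 − 0.20) = 50. Both reproduce. This is a simple two-group calculation and does not depend on the growth model.

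**Identification on two waves, continuous outcome, arm as predictor.**

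- Moments: 2 means + 2 regressions on arm + 2 variances + 1 covariance = 7.
- Parameters: 2 growth means + 2 arm effects + 2 growth variances + 1 growth covariance + 2 residual variances = 9.
- The Jacobian of the implied moments has rank 7, so the model is not identified.
- Equal residual variances: 8 parameters, rank 7. Also dropping the path from arm to intercept: 7 parameters, rank 6. Neither is identified.
- Covariates do not help. Each column adds 2 moments and 2 paths, so the shortfall of 2 (or 1) stays.
- The failure is in the variance part: 3 moments against 5 parameters, or 4 with equal residuals. The path from arm to slope was identified in every version.
- Versions that run include a fixed slope (7 parameters, or 6 with equal residuals) and a random slope with zero residuals (7).
- Three waves: 12 moments, 10 parameters, full rank.

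**What the open choices do to the estimate.** Let rho be the T1-T3 correlation and k = SD(T1)/SD(T3). The documents give neither, so both are assumed. Estimates are in T3 SDs and data are complete.

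- *Arm on intercept and slope.* Both waves have the same predictors, so the covariance constraint drops out and the estimate is the change-score difference. Maximum likelihood fits to 20 simulated trials under four constraints agreed with it to within 5e-8.
- *Arm on slope only.* With a fixed slope and free residuals, or a random slope and zero residuals, the estimate is ANCOVA, which puts weight rho/k on the baseline difference. With a fixed slope and equal residuals the weight is 2·rho·k/(1 + k²). At k = 0.5, rho = 0.5 these are 1.00 and 0.40, so the two estimates differ with SD 0.60 × 0.5 × √(2/40) = 0.07. At k = 1 they coincide. If rho > k, free residuals imply a negative T1 residual variance; bounded at zero, the fit returns the change score.

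Change score against ANCOVA at 40 per arm: SD of the difference between the estimates = |rho − k| × √(2/40). Variance saved by ANCOVA = 1 − (1 − rho²)/(1 + k² − 2·rho·k). Each cell shows the SD, then the saving.

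| k | rho 0.3 | rho 0.5 | rho 0.7 | rho 0.9 |
|---|---|---|---|---|
| 1 | 0.16, 35% | 0.11, 25% | 0.07, 15% | 0.02, 5% |
| 0.75 | 0.10, 18% | 0.06, 8% | 0.01, 0% | 0.03, 11% |
| 0.5 | 0.04, 4% | 0.00, 0% | 0.04, 7% | 0.09, 46% |

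Simulation (8,000 trials per cell) gave savings within 2 percentage points of these, with ANCOVA about 1% worse in two cells where the formula gives 0%. Where the formula gives an SD of 0.00 or 0.01, simulation gave 0.022, because the formula treats the regression slope as known. Mean estimates agreed to 0.001 in every cell. For weight gain k may be well below 1, since a woman normal-weight before pregnancy who enters at 13-16 weeks is eligible only if she "has gained less than 10 lbs in total for women of normal pre-pregnancy weight", with a 5 lb limit for overweight or obese women.

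**Missing T3 data.** The first equivalence above needs complete data. In 60 simulated trials (50 per arm, 20% of T3 missing, k = rho = 0.5), unstructured and equal-variance fits, both with arm on intercept and slope, differed with SD 0.03 and by at most 0.08.

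**The case against.** The strongest reply is that IV.F says only that growth curve models will be used. It does not name a random slope, a time score or one value per wave, and identified versions exist:

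- A fixed slope runs.
- Fitbit data are daily. Fourteen daily values with independent residuals identify the random-slope model (21 parameters, rank 21).
- Scoring time by gestational age identifies the variance part (rank 5 of 5, against 3 of 5 by wave).
- A third weight, at delivery or before pregnancy, would also identify it.

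This stands to the extent that a reader should not infer that every growth model is impossible here. But the plan assigns none of these to the model, and each has limits. Delivery weight is self-reported and falls after Aim 2's 12-week endpoint. Pre-pregnancy weight is a third occasion only if weight itself is modelled; if gain is modelled, it is zero for everyone. The Fitbit route relies on independent days: one shared week-level variance makes the variance part 18 parameters with rank 17.

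It is also fair to say that the trial is a pilot, that the arm effect is estimable in any case, and that the difference between estimators is small or nil in part of the range. That limits the weight of the point. It does not make the named method fit the two-wave schedule.

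**Conclusion.** The point holds in limited form. In its usual form the growth model named for Fitbit exercise, EGWG and the mediators is not identified on the T1 and T3 data described in IV.A, and the plan gives neither an identifying constraint nor the role of arm at baseline.

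A reader might go further and infer that the intervention effect cannot be estimated, that it would be biased, or that the sample size is wrong. The documents do not support any of these. The arm effect on mean change is identified, all the estimators compared here are unbiased under randomisation, and 40 per arm reproduces.

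The practical cost is in precision and in an estimate open to later choice: about 0% to 46% of variance over the assumed range of rho and k, and an SD of up to 0.16 between the two main estimates, against a design effect of 0.63. The counts assume a continuous outcome with one value per wave and time scored by wave. They do not apply as they stand if EGWG is analysed as the three-level category, and Table 1 could not be checked.

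**What to change.** Amend section IV.F before outcomes are examined by arm:

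1. For continuous outcomes measured only at T1 and T3 (weight gain, Fitbit activity and sleep, eating behaviour, each mediator), replace the growth model with regression of the T3 value on arm adjusted for the T1 value. The alternative is a two-occasion mixed model with a common baseline mean and unstructured covariance, which keeps women with missing T3 data in the model.
2. Keep growth curve models for the LTEQ, the mood scales and the PSQI, and state whether arm predicts the intercept.
3. As secondary clarifications, state whether EGWG is analysed as continuous gain or as the guideline category, and whether self-reported delivery weight lies outside the 12-week model.

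The cost is a small change of wording and analysis. It needs no new data, adds no participant burden and leaves the sample size as it is. SAS, already named in the plan, fits these models.
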